8.1.2 SUBGROUP ANALYSES

Effect modification by pre-specified risk factors for CVD will be investigated by calculating stratum-specific point and interval hazard ratios and by assessing the statistical significance of any differences observed through a partial likelihood ratio test for clustered survival data. The pre-specified sub-groups are age, HDL-C, sex, baseline CVD risk, geographic region, and prevalent diabetes at enrollment. Age will be grouped as <70 and 70+ years of age, and HDL-C and baseline CVD risk will be grouped in tertiles. There are no *a priori* effect modifiers hypothesized, and MACH15 is not powered to detect any. Unless there is strong modification of the treatment effect, the power of this trial to detect any effect modification will be low.

8.1.3 INTERIM ANALYSIS

At the discretion of the Data and Safety Monitoring Board (DSMB), interim analyses will be performed periodically. Each meeting will include an administrative review to assess accrual, retention and the progress of the trial. In addition, there will be a review of efficacy, safety, and the occurrence of any adverse effects. For early stopping for efficacy, it will be suggested that the trial be stopped if the p-value for the log rank test for the primary endpoint and secondary endpoint are both < 0.001, following the Haybittle-Peto rule,^{13,14} and if, in addition, the results for other endpoints, including fatal and non-fatal myocardial infarction (MI), fatal CVD, hospitalized angina, revascularization, ischemic stroke and all-cause mortality are consistent with the results for incident CVD and diabetes. Futility analysis will be done once per year for the duration of the trial up to the sixth year, where at each time, given the observed data up to that point, the probability of observing an effect of the hypothesized value or anything more extreme would be less than 5% for both the pre-specified primary and secondary

endpoint. Safety and adverse events will be carefully monitored, including total and clinical site-specific cancer, hospitalizations, motor vehicle collisions, falls, fall-related fractures, alcohol misuse, atrial fibrillation, hemorrhagic stroke and increase in liver function tests to >2X ULN, and unmasking and stopping for safety will be considered should rates in the intervention arm appear unacceptably elevated compared to the abstention arm, accounting for multiple comparisons and adequate follow-up.

An interim analysis of HDL-C is described in Table 8.4 below. Results of this analysis will also be brought to the DSMB, with a discussion of stopping if no difference in levels between study arms is observed.

8.2 SAMPLE SIZE CALCULATIONS

Sample size calculations involved extensive explorations over a range of primary endpoint definitions and baseline rates, baseline adherence rates and improvements to these due to household network effects, proportions of households with 1, 2 and 3 eligible members, intra-household correlation coefficients, and minimum expected effect sizes.

We originally assumed that our trial will be individually randomized trial, and that the primary combined expanded CVD incidence endpoint in the abstention arm will have a rate of 0.026/person-year, modestly higher than the 2.2% annual rate observed in SPRINT,¹⁵ increased slightly because, unlike SPRINT, we are including diabetic individuals and total mortality as an outcome and excluding CHF alone. Participants will enroll during the first 3 years and then will be followed for an average of 6 years. We have assumed that there will be 1% annual loss to follow-up (LTF) in both groups, and 10% non-adherence at any point in time over follow-up for participants who are the sole person in their household to be randomized, leading, for these participants, to an effective hazard ratio of 0.838 under an assumed true hazard ratio of 0.82 as in Ronksley, et al.¹⁶ Under these assumptions, to provide a minimum of 80% power at a two-sided 0.05 significance level for detecting a 18% relative decrease in the intervention group endpoint rate, for an individually randomized trial design with one participant per household, we will need 3,900 participants per arm,¹⁷ for a total of 7,800.

Although we conservatively powered the trial for an expected relative risk (RR) of 0.82, there is substantial evidence suggesting that for CVD, an RR of 0.75 is likely to be observed. If so, we will have adequate power for baseline rates as low as approximately 0.0125/person-year, significantly lower than the observed rate in MESA.

[figure not shown]
TABLE 8.1: POWER FOR CARDIOVASCULAR DISEASE ANNUAL EVENT RATES

Annual Event Rate	Relative Risk		
	RR=0.82	RR=0.80	RR=0.75
1.4%	55%	65%	84%
1.8%	65%	75%	92%
2.2%	74%	83%	96%
2.6%	80%	88%	98%
3.0%	85%	92%	99%
3.4%	89%	94%	99%

Figure 8.1 presents power for different values of relative risks (0.80, 0.82 and 0.84) as a function of a range of plausible annual events rates (from 0.014/year to 0.035/year).

FIGURE 8.1: POWER FOR PRIMARY ENDPOINT

Power for primary endpoint (n=7,800, 1% annual LTF and 10% non-adherence in single households, 9% in multiple participant households, ICC=0.005, proportion of households with ≥ 2 members=70%, proportion of additional household members eligible=30%)

For the secondary diabetes outcome, with $\alpha=0.05$ and assuming baseline prevalence of diabetes of 25% leading to an available sample size of 5,850, with an assumed diabetes incidence rate of 0.017/person-year in the abstention arm, as consistent with an 8.2% cumulative incidence in MESA over 5 years of follow-up among 45-84 year olds,¹⁸ and with all assumptions as above concerning household clustering parameters, the table below displays the minimum power to detect RR for diabetes under even lower annual diabetes rates than has been assumed.

TABLE 8.2: MINIMUM POWER FOR DIABETES ANNUAL EVENT RATES

Minimum Power for Diabetes (n=5,850, 1% annual LTF and 10% non-adherence in single households, 9% in multiple participant households, ICC=0.005, proportion of households with ≥ 2 members=70%, proportion of additional household members eligible = 30%)			
Annual Event Rate	Relative Risk		
	RR=0.80	RR=0.75	RR=0.70
1.3%	50%	70%	85%
1.5%	55%	75%	90%
1.7%	60%	80%	93%

The trial will be adequately powered to detect relative risks of 0.75 and lower for diabetes over a plausible range of baseline event rates, assuming a baseline prevalence of 25%. The proportion of participants who have diabetes at baseline will not change the power to detect the primary outcome, but it will change the power to detect the effect of alcohol on risk of diabetes, the secondary study outcome. If the proportion of participants with diabetes at baseline is 30% rather than 25%, we will have power to detect a RR of 0.74 instead of 0.75 if the background incidence rate is 1.7%/person/year as expected, 0.73 instead of 0.74 if the background rate is 1.5%, and 0.71 instead of 0.72 if the background rate is as low as 1.3%. If the proportion of enrolled participants with prevalent diabetes exceeds expectation, potential limits to enrollment may be considered in conjunction with the DSMB to ensure adequate power for this outcome (see Section 8.5).

TABLE 8.3: MAXIMUM DETECTABLE RELATIVE RISK FOR DIABETES

Maximum Detectable Relative Risk for Diabetes (1% annual LTF and 10% non-adherence in single households, 9% in multiple participant households, ICC=0.005, proportion of households with ≥2 members=70%, proportion of additional household members eligible = 30%)		
	n=5,850 (25% baseline diabetes prevalence)	n=5,460 (30% baseline diabetes prevalence)
1.3%	0.72	0.71
1.5%	0.74	0.73
1.7%	0.75	0.74

During the vanguard phase, it will be essential to demonstrate that the minimum annual adherence rates are in place, to ensure adequate power. Hence, although HDL-C levels may or may not be part of the mechanism by which alcohol intake affects cardiovascular and diabetes risk, HDL-C is known to be an excellent marker of alcohol intake.¹⁹ Therefore, to assess adherence during the vanguard phase, we will compare the change in HDL-C over an approximately 6 month period between the two trial arms. Based on a two sample t-test for comparing the difference between the changes in the intervention and abstention groups, the minimum detectable change in HDL that could be expected for 80% power, assuming that there is no change in the abstention group, is given. We consider an assessment of adherence after 1,000 participants have been enrolled in total at the 7 vanguard clinical sites that are followed for at least 3 months. Assuming that the range of the standard deviation of the change in the HDL will be from 5 mg/dl to 8.5 mg/dl, corresponding to a 50% range around the median value, 6.7 mg/dl, reported by the meta-analysis by Rimm et al.,¹⁹ the minimum detectable difference between average changes in HDL cholesterol in the two groups in absolute values and in percents, for 80% power are given in the table above.

TABLE 8.4: CHANGE IN HIGH DENSITY LIPOPROTEIN-CHOLESTEROL

Standard deviation of the change in HDL-cholesterol	Minimum detectable change (n=1,000)	
	mg/dl	%
5	0.89	1.9
6.5	1.15	2.4
8	1.42	3.0
8.5	1.51	3.1

In the comprehensive meta-analysis of change in HDL-C in relation to alcohol intake based on 25 studies,¹⁹ it was found that a 41 g/day alcohol over an average of 4 weeks was related to a 5.1 mg/dl increase in HDL-C. For a dose of approximately 15 g/day, we would expect a 1.5 mg/dl increase in HDL-C over 3 months of observation in the first year. Clearly, we will have adequate power to detect this difference, even if the standard deviation for the change in HDL-C is on the highest end of what might be reasonably expected.

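### Section 8.2: the power tables are right, but two summary sentences, on diabetes power and on the diabetic share and primary power, say more than the section's own figures support

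*Combined protocol and SAP*

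**What the plan says.** Section 8.2 sizes the trial "to provide a minimum of 80% power at a two-sided 0.05 significance level for detecting a 18% relative decrease" in the primary outcome. For incident diabetes it proceeds by "assuming baseline prevalence of diabetes of 25% leading to an available sample size of 5,850". The yearly incidence among abstainers is put at 1.7%.

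For RR 0.75, Table 8.2 prints power of 70%, 75% and 80% at 1.3%, 1.5% and 1.7% per year. Table 8.3 prints maximum detectable RRs of 0.72, 0.74 and 0.75 at the same rates with 25% prevalence, and 0.71, 0.73 and 0.74 with 30%.

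The paragraph between the tables concludes: "The trial will be adequately powered to detect relative risks of 0.75 and lower for diabetes over a plausible range of baseline event rates", on the 25% prevalence assumption. It then gives the detectable RRs at 30% prevalence, including "0.73 instead of 0.74 if the background rate is 1.5%, and 0.71 instead of 0.72 if the background rate is as low as 1.3" per cent. It also states: "The proportion of participants who have diabetes at baseline will not change the power to detect the primary outcome". It adds that limits to enrolment may be considered with the DSMB if prevalent diabetes exceeds expectation.

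Earlier in the same section, the primary event rate is set at 2.6% per year against 2.2% in SPRINT, "increased slightly because, unlike SPRINT, we are including diabetic individuals and total mortality as an outcome and excluding CHF alone".

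**The concern.** The diabetes sentence summarises a table in which RR 0.75 falls short of 80% at two of the three rates shown. A reader who takes the sentence alone will think the diabetes objective has more margin against a low incidence than it has. This matters beyond the secondary analysis, because Section 8.1.3 makes both the efficacy-stopping and the futility criteria depend on the secondary endpoint as well as the primary.

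The second sentence denies a link that the event-rate rationale relies on. If diabetic participants raise the primary event rate, their share affects the number of primary events and hence primary power. The denial stands in the paragraph that raises a possible limit on diabetic enrolment, so such a limit could be discussed as though it had no bearing on the primary outcome.

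**Working it through.** **Inputs from the documents.** Two-sided alpha 0.05 (8.2; two-sidedness is stated for the primary and carried over to diabetes); 1:1 allocation; 1% annual loss to follow-up; 10% non-adherence; mean follow-up 6 years, range 4.5-7.5 (11.4); n = 7,800 × 0.75 = 5,850, or 7,800 × 0.70 = 5,460 at 30% prevalence. The 1.7% rate agrees with its source: −ln(1 − 0.082)/5 = 0.0171 per year.

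**Dilution.** Section 8.2 turns a true 0.82 into an effective 0.838, which is HR_eff = 1 − 0.9 × (1 − HR). For RR 0.75, HR_eff = 0.775 and |ln HR_eff| = 0.2549.

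**Events and power.** Per arm, with hazard λ, loss hazard 0.01 and 6 years:

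events = (n/2) × λ/(λ + 0.01) × (1 − exp(−6(λ + 0.01)))

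power = Φ(½ √d × |ln HR_eff| − 1.96), where d is total events.

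At 1.7%: abstention arm 2,925 × 0.0942 = 275; alcohol arm (λ = 0.017 × 0.775 = 0.01318) 2,925 × 0.0738 = 216; d = 491. Power = Φ(½ × 22.16 × 0.2549 − 1.96) = Φ(0.864) = 80.6%.

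| Rate per year | d | Power, RR 0.75 | Table 8.2 |
|---|---|---|---|
| 1.3% | 380 | 70.0% | 70% |
| 1.5% | 436 | 75.8% | 75% |
| 1.7% | 491 | 80.6% | 80% |

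Spreading follow-up over 4.5-7.5 years moves these by at most 0.1 point. Household clustering (ICC 0.005) and the 9% non-adherence in multi-participant households are left out; including them moves the results by less than half a point. All nine cells of Table 8.2 reproduce within 1 point.

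**Threshold for RR 0.75.** 80% power needs d = 4 × (1.96 + 0.842)² / 0.2549² ≈ 483 events. With n=5,850 this is reached at about 1.67% per year.

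**Table 8.3.** It names no power level. Solving for 80% gives 0.720, 0.738 and 0.752 (n=5,850) and 0.711, 0.729 and 0.744 (n=5,460), which match the printed values. The protocol's own table therefore uses the 80% standard.

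**30% prevalence.** With n=5,460, power for RR 0.75 is 66.9%, 72.9% and 77.8% at 1.3%, 1.5% and 1.7%.

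**Primary outcome.** With HR_eff 0.838 and n=7,800, the same method gives 73.8% at 2.2% per year and 80.2% at 2.6% (Table 8.1: 74% and 80%). The documents give no diabetic to non-diabetic rate ratio k, so k is assumed to lie between 1.25 and 2.0, with 2.6% holding at a 25% share. At share s:

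rate = 0.026 × (1 + s(k − 1)) / (1 + 0.25(k − 1))

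| k | Rate at 30% share | Power at 25% | Power at 30% | Change |
|---|---|---|---|---|
| 1.0 | 2.60% | 80.2% | 80.2% | 0 |
| 1.25 | 2.63% | 80.2% | 80.6% | +0.4 |
| 1.5 | 2.66% | 80.2% | 81.0% | +0.8 |
| 2.0 | 2.70% | 80.2% | 81.6% | +1.4 |

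Only k = 1 leaves primary power unchanged.

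**The case against.** On diabetes, nothing is concealed. Table 8.2 stands directly above the sentence, and the detectable RRs by rate follow in the same paragraph and in Table 8.3. The 1.7% rate is the expected rate, and the table is introduced as covering rates below it, so it works as a downside check. The term for the range of rates is never defined. Section 1.2.3 cites a risk reduction approaching 30%, and RR 0.70 has 85%, 90% and 93% power at the three rates. All of this stands and limits the size of the point. It does not rescue the sentence: 1.3-1.7% is the only range shown, no higher rate is tabulated, and 80% is the only power level that Section 8.2 names.

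On the primary outcome, the sentence can be read as being about denominators: prevalent diabetes removes people from the diabetes analysis but not from the 7,800. That is true. A rate ratio near 1 also cannot be excluded, since Section 4.2 requires every participant to be at high risk and diabetes status feeds the risk score (Table 6.1, note 6). But log-rank power depends on events, and the section itself cites diabetic participants as a reason for a higher rate.

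A reader might infer that a limit on diabetic enrolment would push the primary outcome below its target. The documents do not support this. A limit is contemplated only if prevalence exceeds expectation, and a return to 25% brings power back to the planned level of about 80%. Nor can the whole step from 74% to 80% in Table 8.1 be put down to diabetic participants, because the higher rate is credited jointly to them, to total mortality and to the exclusion of CHF alone.

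**Conclusion.** Two summary sentences conflict with the section's own figures; the tables are correct.

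- **Diabetes.** At 25% prevalence, RR 0.75 has 80% power only from about 1.67% per year. Over the tabulated rates, the supportable claim is RR 0.72 or lower (0.71 at 30% prevalence). The shortfall is confined to RRs between about 0.72 and 0.75. It would be wrong to conclude that the diabetes objective is underpowered as designed: at the assumed rate and prevalence, RR 0.75 does have 80%. This part rests only on printed figures and the 80% standard.
- **Primary.** The flat denial contradicts the event-rate rationale in logic and direction. Its size is not in the documents; the 0.4-1.4 points for 30% versus 25% rest wholly on the assumed rate ratios and on 2.6% holding at a 25% share.

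Severity is minor to moderate.

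**What to change.** Replace the diabetes sentence with:

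> At 25% baseline prevalence the trial has 80% power for RR 0.75 at the assumed rate of 1.7%/year; over 1.3-1.7%/year, at least 80% power is available only for RRs of about 0.72 or lower (0.71 or lower at 30% prevalence), and power for RR 0.75 is 70% at 1.3% and 75% at 1.5%.

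Replace the statement on the diabetic proportion with:

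> The diabetic proportion does not change the number analysed for the primary outcome, but it may change primary power through the event rate, so any limit on diabetic enrolment should be considered with its projected effect on primary events.

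The cost is two sentences, plus one projection of primary events if a limit is ever put to the DSMB. The sample size, tables and analysis stay as they are; the stated diabetes power simply becomes slightly less favourable.

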8.3 RECRUITMENT RATE

The accrual period in MACH15 is 3 years and during this period the rate of accrual will be monitored on a monthly basis. We expect a recruitment rate on average of 11 new participants/clinical site/month. If the observed rate falls appreciably below the projected level, the reasons will be identified and remedial actions taken to protect the power of the trial and alleviate concerns about selective entry and other aspects of quality.

8.4 RANDOMIZATION METHOD

We propose permuted block randomization with random block lengths. Following the design of the Look AHEAD Trial,²⁰ we will randomize participants stratified by clinical site using a block randomization structure with randomly permuted block sizes of 4 and 8, to ensure balanced allocation and to avoid participant allocation being predictable,²¹ as can occur with single-size block allocations. Alternative randomization methods exist (e.g., complete, simple, urn, and covariate adaptive); however, such schemes can lead to imbalance if, for example, inclusion criteria change midway through recruitment in response to new data from other trials or changes in guidelines. Use of additional, less important stratification factors is not generally recommended for trials the size of MACH15²² and may delay randomization until data are entered and verified. In a trial of this size, doing so introduces additional operational complexities, with little expected gain in balance by these factors.

The randomization protocol and the randomization process will be prepared and executed by investigators from the Data Management Center (DMC) through the secure web-based data management system, so that eligibility is automatically confirmed. The trial statisticians will revise the randomization protocol to ensure that sufficient baseline and eligibility data are entered and validated before participants are randomized into the trial. In addition, the trial statisticians will closely monitor the intervention allocations by clinical site to ensure protocols are being adhered to and balance is being maintained.

8.5 DATA SAFETY MONITORING BOARD REPORTS

The progress of MACH15 and the trial's potential for attaining its goals will be regularly evaluated by the DSMB. The feasibility of the trial will be formally assessed by the DSMB early in the trial prior to initiation to ensure that the trial interventions are being safely delivered.

The DSMB will oversee the safety of participants and will provide oversight of the trial with respect to its primary aims. Following the protocol approval, the DSMB will periodically review and evaluate data on recruitment, quality control, compliance, adverse events, and outcomes. The DSMB may recommend corrective action, changes in the protocol, early stopping of the trial or parts of the trial. Each meeting will include an administrative review to assess accrual, retention, and the progress of the trial. In addition, there will be a review of efficacy, safety, and the occurrence of any SAEs or MACH15 AEs. The DSMB will also review and advise on proposed changes to the protocol. The Statistical Coordinating Core (SCC) will be the primary group interacting with the DSMB, preparing reports, and responding to queries.

The approach that developed to efficiently prepare DSMB reports includes a large number of statistical tables, flow-charts and plots. By maintaining a spreadsheet on a shared drive with tables and figures identified in the table of contents, statisticians indicate what has been completed and enter the location of the associated files. Any SCC member can review masked progress on the report at any time, and when it is complete, the program coordinator will run an application which quickly creates a draft document, including a table of contents. Other material can be added to the draft, and later changes to single tables or graphs can be incorporated individually. Once the technical material is ready (typically 2 weeks from the data freeze), a complete draft is assembled. In addition, we will use a website security model that can allow DSMB members restricted access to designated pseudonymised material.

Comprehensive data on all quality control activities will be included. Comparisons of measures of distribution of values over time, and among clinical sites or instruments will also be included. The SCC will develop and maintain standards to identify outliers, and to initiate and coordinate separate review of these for accuracy.

Reports to the DSMB are planned for every six months once recruitment is initiated. Hard copy open and closed reports will be generated for the DSMB and open reports for the Project Officer. Open reports will also be sent to the DMC and Clinical Coordinating Core leadership, and a subset of these will be continually updated on the trial website. These will allow for verification of completeness, timeliness, reliability, and accuracy of collection and coding of data.

9.1 TRIAL WEBSITE OVERVIEW

All MACH15 clinical sites will use the World Wide Web (WWW) to enter MACH15 data collected from participants. Each clinical site will have a password protected area on the MACH15 home page through which data will be entered. Documentation of the data entry system will be maintained at the Data Management Center (DMC). In addition, training materials for clinical site staff will be available in a downloadable format on the MACH15 website (www.mach15trial.org). Site-specific reports relating to aggregate participant demographics, recruitment goals, screening yield, among other reports, will be available on the website based on live data and available 24/7. All data are password protected, with individual passwords for each person with access to the clinical site. Access is limited on an individual basis depending on each person's associated clinical site and role in the trial.

Data security is paramount in the digital age in which we live and work; 2048 bit signatures and up to 256 encryption, and Instant SSL certificates offer the highest possible levels of security. This meets or exceeds security recommendations specified by the National Institute of Standards and Technology (NIST). All communication between the users and the MACH15 website are encrypted to prevent unauthorized viewing of any trial information. All servers are housed at a state-of-the-art data center a few miles from the DMC campus, with strong physical security controls to prevent unauthorized access to the servers and storage. A two-part disaster back-up program is employed, in which trial data is backed up nightly to institutional back-up resources, as well as an internal departmental back-up system which acts as a secondary recovery point. In the event that the primary back-up system is unavailable to restore critical data, data can be restored from the secondary point. The secondary back-up also provides back-up copies in an offsite location, kept in a locked, fire and waterproof storage cabinet away from the data center. Clinical sites will have local procedures in place for back-up and recovery of data following a disaster.

